### 7.5 Visit 5: Interim Visit (Week 16 / Day 113 ± 3 Days)

The following procedures will be performed at Visit 5:

- 1. Results of laboratory evaluations will be reviewed
- 2. The Subject's diary provided at the previous visit will be reviewed.
- 3. A urine pregnancy test will be conducted for all females of childbearing potential (see Section 5.4)

May 20, 2022 Protocol: **AS012-20-01** Page 38 of 88

- 4. The use of concomitant medications since the previous study visit will be documented and assessed. (See Section 5.6)
- 5. Vital signs (blood pressure, pulse, respiratory rate and oral body temperature) will be documented. Subjects must remain in a seated or supine position for at least 5 minutes before vital signs are obtained. (See Section 5.3)
- 6. A urinalysis dipstick will be performed and evaluated (See Section 5.5)
- 7. A blood sample will be collected for Hematology and Chemistry (See Section 5.5)
- 8. The occurrence of all AEs will be assessed and documented following the procedures in Sections 5.7, 10.1, and 10.3.
- 9. Visit 6 (Study Day 141 ± 3 Day) will be scheduled and the Subject will be instructed to bring the Subject diary with him or her to this visit.

# 7.6 Visit 6: Interim Visit (Week 20 / Day 141 ± 3 Days)

# The following procedures will be performed at Visit 6:

- 1. Results of laboratory evaluations will be reviewed
- 2. The Subject's diary provided at the previous visit will be reviewed.
- 3. A urine pregnancy test will be conducted for all females of childbearing potential (see Section 5.4)
- 4. The use of concomitant medications since the previous study visit will be documented and assessed. (See Section 5.6)
- 5. A physical examination will be performed. At a minimum, the physical examination will include the following: weight, assessment of general appearance, comprehensive skin examination, HEENT, heart, lungs, musculoskeletal system, lymph nodes, neurological systems, abdomen, and extremities. (See Section 5.2)
- Vital signs (blood pressure, pulse, respiratory rate and oral body temperature) will be documented. Subjects must remain in a seated or supine position for at least 5 minutes before vital signs are obtained. (See Section 5.3)
- 7. A urinalysis dipstick will be performed and evaluated at a site (See Section 5.5)
- 8. A blood sample will be collected for Hematology and Chemistry (See Section 5.5)
- 9. The occurrence of all AEs will be assessed and documented following the procedures in Sections 5.7, 10.1, and 10.3.
- 10. Visit 7 (Study Day 169 ± 3 Day) will be scheduled and the Subject will be instructed to bring the Study Product (used, unused, and partially used) and Subject diary with him or her to this visit.

# 7.8 Visit 8: Interim Visit (Week 28 / Day 197 ± 3 Days)

# The following procedures will be performed at Visit 8:

- Results of laboratory evaluations will be reviewed
- 2. The Subject's diary provided at the previous visit will be reviewed.
- 3. A urine pregnancy test will be conducted for all females of childbearing potential (see Section 5.4)
- 4. The use of concomitant medications since the previous study visit will be documented and assessed. (See Section 5.6)
- 5. Vital signs (blood pressure, pulse, respiratory rate and oral body temperature) will be documented. Subjects must remain in a seated or supine position for at least 5 minutes before vital signs are obtained. (See Section 5.3)
- 6. A urinalysis dipstick will be performed and evaluated (See Section 5.5)
- 7. A blood sample will be collected for Hematology and Chemistry (See Section 5.5)
- 8. The occurrence of all AEs will be assessed and documented following the procedures in Sections 5.7, 10.1, and 10.3.
- Visit 9 (Study Day 253 ± 3 Day) will be scheduled and the Subject will be instructed to bring the Study Product (used, unused, and partially used) and Subject diary with him or her to this visit.
- 10. A phone call will be scheduled at the study week 32 to collect information on the study drug use, health changes and concomitant medication

### 7.9 Visit 9: Interim Visit (Week 36 / Day 253 ± 3 Days)

### The following procedures will be performed at Visit 9:

[figure not shown]
- 1. Results of laboratory evaluations will be reviewed
- 2. A urine pregnancy test will be conducted for all females of childbearing potential (see Section 5.4)
- 3. The use of concomitant medications since the previous study visit will be documented and assessed. (See Section 5.6)
- 4. The Subject's diary provided at the previous visit will be collected and reviewed.
- 5. The returned study drugs will be counted
- 6. Vital signs (blood pressure, pulse, respiratory rate and oral body temperature) will be documented. Subjects must remain in a seated or supine position for at least 5 minutes before vital signs are obtained. (See Section 5.3)
- 7. A urinalysis dipstick will be performed and evaluated (See Section 5.5)
- 8. A blood sample(s) will be collected for Hematology and Chemistry (See Section 5.5)
- 10. Subjects will be instructed to take the study drug with approximately 240 mL (8 oz.) of water. Tablets should be swallowed intact and not chewed or crushed. (See Section 8.6)

May 20, 2022 Protocol: **AS012-20-01** Page 41 of 88

- 11. The occurrence of all AEs will be assessed and documented following the procedures in Sections 5.7, 10.1, and 10.3.
- 12. A 12-lead electrocardiogram (ECG) will be performed (See Section 5.9)

14. Focused Area Assessments will be performed for:

- 15. The following will be dispensed:
  - The IP kit assigned for Visit 9 by IRT
  - A diary card with instructions and to record health changes and concomitant medication
- 16. Visit 10 (Study Day 309 ± 3 Days) will be scheduled and the Subject will be instructed to bring the Subject diary with him or her to this visit.
- 17. A phone call will be scheduled at the study week 40 to collect information on the study drug use, health changes and concomitant medication

# 7.10 Visit 10: Interim Visit (Week 44 / Day 309 ± 3 Days)

The following procedures will be performed at Visit 10:

- Results of laboratory evaluations will be reviewed
- 2. The Subject's diary provided at the previous visit will be reviewed.
- 3. A urine pregnancy test will be conducted for all females of childbearing potential (see Section 5.4)
- 4. The use of concomitant medications since the previous study visit will be documented and assessed. (See Section 5.6)
- A physical examination will be performed. At a minimum, the physical examination will include the following: weight, assessment of general appearance, comprehensive skin examination, HEENT, heart, lungs, musculoskeletal system, lymph nodes, neurological systems, abdomen, and extremities. (See Section 5.2)
- 6. Vital signs (blood pressure, pulse, respiratory rate and oral body temperature) will be documented. Subjects must remain in a seated or supine position for at least 5 minutes before vital signs are obtained. (See Section 5.3)

May 20, 2022 Protocol: **AS012-20-01** Page 42 of 88

- 7. A urinalysis dipstick will be performed and evaluated (See Section 5.5)
- 8. A blood sample will be collected for Hematology and Chemistry (See Section 5.5)
- 9. The occurrence of all AEs will be assessed and documented following the procedures in Sections 5.7, 10.1, and 10.3.
- Visit 11 (Study Day 337 ± 3 Day) will be scheduled and the Subject will be instructed to bring the Study Product (used, unused, and partially used) and Subject diary with him or her to this visit.

# 7.11 Visit 11: Interim Visit (Week 48 / Day 337 ± 3 Days)

# The following procedures will be performed at Visit 11:

- 1. Results of laboratory evaluations will be reviewed
- 2. The Subject's diary provided at the previous visit will be collected and reviewed.
- 3. The returned study drugs will be counted
- 4. A urine pregnancy test will be conducted for all females of childbearing potential (see Section 5.4)
- 5. The use of concomitant medications since the previous study visit will be documented and assessed. (See Section 5.6)
- 6. A physical examination will be performed. At a minimum, the physical examination will include the following: weight, assessment of general appearance, comprehensive skin examination, HEENT, heart, lungs, musculoskeletal system, lymph nodes, neurological systems, abdomen, and extremities. (See Section 5.2)
- 7. Vital signs (blood pressure, pulse, respiratory rate and oral body temperature) will be documented. Subjects must remain in a seated or supine position for at least 5 minutes before vital signs are obtained. (See Section 5.3)
- 8. A urinalysis dipstick will be performed and evaluated (See Section 5.5)
- 9. A blood sample will be collected for Hematology and Chemistry (See Section 5.5)
- 10. The occurrence of all AEs will be assessed and documented following the procedures in Sections 5.7, 10.1, and 10.3.
- 11. The following will be dispensed:
  - The IP kit assigned for Visit 11 by IRT
  - A diary card with instructions and to record health changes and concomitant medication
- Visit 12 (Study Day 365 ± 3 Day) will be scheduled and the Subject will be instructed to bring the Study Product (used, unused, and partially used) and Subject diary with him or her to this visit.

# 7.12 Visit 12: End of Treatment Visit (Week 52 / Day 365 ± 3 Days)

# The following procedures will be performed at Visit 12:

[figure not shown]
- 1. Results of laboratory evaluations will be reviewed
- 2. A urine pregnancy test will be conducted for all females of childbearing potential (see Section 5.4)
- 3. The use of concomitant medications since the previous study visit will be documented and assessed. (See Section 5.6)

May 20, 2022 Protocol: **AS012-20-01** Page 43 of 88

[figure not shown]
- 4. The Subject's diary provided at the previous visit will be collected and reviewed.
- 5. The returned study drugs will be counted
- 6. A physical examination will be performed. At a minimum, the physical examination will include the following: weight, assessment of general appearance, comprehensive skin examination, HEENT, heart, lungs, musculoskeletal system, lymph nodes, neurological systems, abdomen, and extremities. (See Section 5.2)
- 7. Vital signs (blood pressure, pulse, respiratory rate and oral body temperature) will be documented. Subjects must remain in a seated or supine position for at least 5 minutes before vital signs are obtained. (See Section 5.3)
- 8. A urinalysis dipstick will be performed and evaluated (See Section 5.5)
- 9. A blood sample(s) will be collected for Thyroid function, Hematology, Chemistry, Coagulation profile, and Lipid Profile (See Section 5.5)

- 12. Subjects will be instructed to take the study drug with approximately 240 mL (8 oz.) of water. Tablets should be swallowed intact and not chewed or crushed. (See Section 8.6)
- 13. The occurrence of all AEs will be assessed and documented following the procedures in Sections 5.7, 10.1, and 10.3.
- 14. A 12-lead electrocardiogram (ECG) will be performed (See Section 5.9)

17. Focused Area Assessments will be performed for:

May 20, 2022 Protocol: **AS012-20-01** Page 44 of 88

- 19. The following will be dispensed:
  - A diary card with instructions and to record health changes and concomitant medication
- 20. Follow-Up Visit 13 (Study Day 449 ± 3 Days) will be scheduled and the Subject will be instructed to bring the Subject diary with him or her to this visit.

# 7.14 Phone call on use of study drug (Weeks 8, 32, and 40)

Phone calls will be scheduled at the study weeks 8, 32, and 40 to collect information on the study drug use, health changes and concomitant medication

# 7.15 Unscheduled Visits and Early Discontinuation Visit

An Unscheduled Visit is allowed at any time, for any reason, if in the Principal Investigator's opinion it is warranted. If the Unscheduled Visit is due to an AE, the Principal Investigator will determine whether additional visits are needed.

If a Subject is discontinued from the study during an Unscheduled Visit, the Unscheduled Visit will be referred to as an Early Discontinuation Visit:

- 1. A urine pregnancy test will be conducted for all females of childbearing potential (see Section 5.4)
- 2. The use of concomitant medications since the previous study visit will be documented and assessed. (See Section 5.6)
- 3. The occurrence of all AEs will be assessed and documented following the procedures in Sections 5.7, 10.1, and 10.3

Additional assessments may be performed per the Investigator's decision.

For all the subjects who discontinue the study prior to Visit 7 all efforts should be made to conduct a visit at, or close to week 24 to collect focused area assessments. Regardless of the reason, Subjects discontinued from IP prior to the end of study will be required to complete the End of Study (EoS) assessment within 2 weeks after the last dose.

If the Subject's condition has worsened to the degree that it is unsafe for the Subject to continue in the study, the Subject may be discontinued from the study as treatment failure and a standard of care treatment may be advised at the Principal Investigator's discretion.

### 8 INVESTIGATIONAL PRODUCT

### 8.1 Description

All study medications will be dispensed by and returned to a qualified dispenser designated by the Principal Investigator. The investigational product will be dispensed only from the institution(s) approved by an Institutional Review Board (IRB) or Independent Ethics Committee (IEC).

The Investigational Product will be supplied by the Sponsor. The following treatments will be self-administered or administered by the Subject's caregiver during this study.

Investigational Products:

AS012 Tablets

Control:

Placebo of AS012 product

## 8.2 Storage Conditions

All study products should be stored in a limited access area, between 15°C and 30°C (59°F and 86°F), protect from bright light.

### 8.3 Packaging and Labeling

In order to maintain the study blind the randomization schedule will be generated by a third party. Randomization will be performed according to a computer-generated randomization scheme. Only

May 20, 2022 Protocol: **AS012-20-01** Page 46 of 88

one Subject number will be assigned to each Subject. The Subject will maintain the same number throughout the study. The Investigational Product will be provided in identically labeled and packaged such that neither the Subject nor any Investigator can identify the treatment.

Each container will be labeled with a two-part, double blind label and will display the following text: "content statement, protocol number, subject number, instructions for use and storage, Sponsor's name, an investigational use statement and warnings: "Keep out of reach of children". Part 2 of the label will contain a sealed copy of the randomization scheme (as a scratch off portion of the product label). This label should be detached from the container prior to dispensing to the Subject and retained at the study site, to be opened in case of medical emergency only. Where possible, the Medical Monitor should be contacted before breaking the blind for any Subject. The Sponsor must be notified in the event the blind is broken.

To maintain the study blind the labels for IP boxes and bottles will include the same content description "Placebo and/or Active AS012 Tablets".

# 8.4 Treatment Assignment

The subject number will correspond to a computer-generated randomization schedule assigning that number to one of the study treatment groups in Part I. The randomization scheme will be generated that the Placebo, assigned in a 3:3:1:3:1 or in 1:1:3:1:1 ratio. The randomization ratio will be changed after enrolling of approximately 55% of subjects.

In Part II (week 24 to week 52) subjects initially randomized to placebo will be re-randomized to AS012 in 1:1 ratio. Subjects originally randomized to AS012 doses will remain on their assigned dosing regimen until the end of Part II (week 52). At the study visits 2, 4, 7, 9, and 11 the IP kit number will be assigned to each subject using Interactive Response Technology (IRT).

#### 8.5 Randomization

At visit 2 the subject will be randomized to one of five treatment groups and the subject number will be assigned by an Interactive Response Technology (IRT). At visit 7 the active treatment will be reassigned for the Placebo group by IRT. Randomization and re-randomization will be stratified by stability of disease (stable vs. non-stable)

IRT using global data across all sites.

At visits 2, 4, 7, 9, and 11 the IP kit number corresponding to the subject's treatment group will be assigned by IRT using kit numbers available at a site.

### 8.6 Administration of Investigational Product

Individual doses will be provided in identically packaged bottles. Bottles will be dispensed at study visits 2, 4, 7, 9, and 11 (Baseline and study weeks 12, 24, 36, and 48.

Each Subject will also receive written study instructions, which detail the proper administration method of the Investigational Product and general study instructions. At scheduled visits 2, 4, 7, 9, and 12 (Baseline and study weeks 12, 24, 36, and 52) the study product will be administered under a supervision of the study site personnel.

May 20, 2022 Protocol: **AS012-20-01** Page 47 of 88

Tablets should be swallowed intact and not chewed or crushed. The doses should be taken with approximately 240 mL (8 oz.) of water between meals, approximately one hour after and before meals.

Investigational Product will be used for 365 consecutive days.

Subjects will be required to use diaries to document the date and time of doses, any missed doses and the occurrence of all adverse events.

At each visit during the study, the Investigator or designee should review proper use of the Investigational Product.

In case of vomiting within 30 minutes of taking a dose, the dose shall be repeated. The dose shall not be repeated if vomiting occurs more than 30 minutes after ingestion. If vomiting recurs no new doses should be taken and the subject should contact the site for instructions.

### Missed doses:

The dose will be skipped if the subjects realizes more than 2 hours after the scheduled time-point. All missed doses should be entered by the subject in the patient diary.

More than 14 consecutive days of non-compliance to study medication (i.e. subjects who have missed all doses for more than 14 consecutive days) will result in subject's discontinuation from the study.

# 8.7 Assessment of Compliance

Compliance with scheduled use of Investigational Product will be determined from the Subject's diary. Subjects will be instructed to bring their daily diary and used and unused study drug containers at all scheduled visits or Early Discontinuation Visit to allow for tablet count and compliance checks. Subjects will also be asked to record in a daily diary the date and time at which they took the study drug. In addition, Subjects will be instructed to document all AEs on the diary.

If the subject does not return the Diary, Subject-reported dosing compliance will be recorded in the source notes and will be used to derive compliance between those visits.

For scheduled visits greater than 4 weeks apart, subjects will be called (at w8, w32, w40) and asked about compliance with study drug.

### 8.8 Investigational Product Accountability

It is the responsibility of the Principal Investigator to ensure that the current disposition of the Investigational Product is maintained at each study site where Investigational Product is inventoried and dispensed. When a drug shipment is received at a study site, the Principal Investigator or the Principal Investigator's Designee must inventory the drug and sign the receipt form provided with the shipment. The receipt form should be emailed as per instructions provided on the receipt. A copy of the receipt should remain at the site.

The Investigator will not supply study test articles to any person not enrolled in this study, or to any physician or scientist except those named as sub-investigators.

A Drug Accountability Log will assist study site staff in maintaining inventory records of study drug.

Subjects must return used, partially used or unused Investigational Product so that any remaining drug supplies can be accounted for and noted in the Drug Accountability Log.

# 8.9 Return of Clinical Supplies

All used and unused containers of Investigational Product may be returned to the Drug Shipping Facility for destruction or be destructed at the site after study close-out and final drug accountability is reconciled.

[figure not shown]
May 20, 2022 Protocol: **AS012-20-01** Page 48 of 88

#### 9. STATISTICAL METHODS

# 9.1 Scientific and Statistical Considerations of the Study Design

This study to assess the efficacy and safety of AS012 in the treatments of non-segmental vitiligo is designed based on recommendations provided by the FDA in PIND 147209 Guidance Meeting (03/05/2020, Reference ID 4571020) regarding the scope and design of studies for this new product.

#### 9.1.1 Rationale for Dose Selection

based on the pre-clinical toxicology studies conducted to date. In the genotoxicity studies, AS012 showed no mutagenic potential.

# 9.1.2 Rationale for the Use of Comparator

A placebo control arm is included to demonstrate that the investigational products are active and as a parameter that the study is sufficiently sensitive to detect differences between products. However, to ensure that patients in the placebo arm receive treatment, they will be re-randomized at Week 24 to receive either

### 9.2 Sample Size Rationale

The study will randomize approximately 320 subjects into 5 treatment arms (n=approximately 64 subjects per arm) in a 1:1:1:1 ratio. The sample size assumes a drop-out rate of about 20%, with 52 evaluable subjects per treatment arm at the time of analysis. The study is powered at 85%, and assumes a two-sample Z-test with equal variances, two-sided alpha ( $\alpha$ ) of 0.05, a Baseline VASI mean of 15.7 and standard deviation of 8.9 (Hamzavi et al, 2004) and an improvement at Week 24 of 35% ( $\Delta$  5.50) for AS012 versus an improvement for placebo of 10% ( $\Delta$  1.56), for a mean treatment difference of 3.94. Since the correlation between Baseline and Week 24 VASI scores is expected to be >0.5, the standard deviation of the difference is conservatively estimated at 70% of the Baseline SD, or 6.4. Randomization will be stratified by stability of disease (stable vs. non-stable)

With a total of six possible stratification levels, 52 evaluable subjects per treatment arm ensures at least 8 subjects per stratification level.

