### Efficacy Analysis

The primary efficacy endpoint will be evaluated using the Intent-to-Treat (ITT) Population. The primary endpoint method of analysis will use an Analysis of Covariance (ANCOVA) model to compare change from baseline in VASI score results between treatment arms at Week 24. The ANCOVA model will include fixed effects for treatment, stability of disease (stable vs. non-stable),

baseline VASI score as a covariate. Point estimates and 95% confidence intervals will be obtained for the difference between each active dose versus placebo.

Missing VASI data at Week 24 will be addressed in the model using multiple imputation methods.

Secondary efficacy variables will be analyzed similarly, however without using multiple imputation methods.

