# Interim Analysis (IA)

No formal Interim Analysis will be performed for this study.

Part I analysis will include all safety and efficacy assessments conducted at week 24. Analysis outputs will be generated when the last subject has completed 24 weeks of study participation, and may include results for all available visits/data. After Part I database lock, subject-level unblinded information will be confined to a designated unblinded study team. A separate document/SAP will provide further details related to unblinding of personnel. A designated list of blinded and unblinded study personnel shall be maintained. Part I analysis subject-level data will not be provided to the site staff and the blinded study team.

An additional unblinded analysis could be undertaken at a subsequent time (e.g. after last patient completed week 36/52 visit) by the unblinded study team to assess the efficacy if required based on the sponsor's discretion. If such an analysis is planned to be undertaken the details would be discussed in SAP.

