3.2 Sample Size

The study will randomize approximately 320 subjects into 5 treatment arms (n=approximately 64 subjects per arm) in a 1:1:1:1:1 ratio. The sample size assumes a drop-out rate of about 20%, with 52 evaluable subjects per treatment arm at the time of analysis. The study is powered at 85%, and assumes a two-sample Z-test with equal variances, two-sided alpha (α) of 0.05, a Baseline VASI mean of 15.7 and standard deviation of 8.9 and an improvement at Week 24 of 35% (Δ 5.50) for AS012 versus an improvement for placebo of 10% (Δ 1.56), for a mean treatment difference of 3.94. Since the correlation between Baseline and Week 24 VASI scores is expected to be >0.5, the standard deviation of the difference is conservatively estimated at 70% of the Baseline SD, or 6.4. The sample size takes into account an interim assessment of futility and efficacy, using an O'Brien-Fleming error spending function to determine the boundaries, once the placebo, dose reach 75% completion of the Week 24 VASI assessment. Randomization will be stratified by stability of disease (stable vs. non-stable) With a total of six possible stratification levels, 52 evaluable subjects per treatment arm ensures at least 8 subjects per stratification level.

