6.9.1.2 Primary analysis of the primary endpoint

The primary endpoint will be summarized descriptively by treatment group.

Note that approximately 5 sites will be designated to perform VASI, and VES by two independent assessors to test reliability and validity of the instruments (see Section 6.9.2.7). Only the assessment by the first assessor will be used for the primary endpoint.

The primary endpoint will be analyzed with an Analysis of Covariance (ANCOVA) model to compare change from baseline in VASI score results between treatment arms at Week 24. The ANCOVA model will include fixed effects for treatment, stability of disease (stable vs. non-stable at screening), and baseline VASI score as a covariate. Point estimates and 95% confidence intervals as well as p-values for the hypothesis of no difference will be obtained for the difference between each active dose versus placebo.

Type I error will be preserved in the primary efficacy analysis by use of a closed test step-down approach. Beginning with the highest total daily dose, pairwise comparisons to placebo will be made in the following sequence:

Number and percentage of subjects achieving these endpoints will be presented by treatment group along with 95% confidence interval for percentages based on binomial proportion.

Maintenance of these endpoint will be assessed by presenting the number and percentage of subjects maintaining these endpoints at Week 64 among those who achieved them at Week 52.

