7. INTERIM ANALYSIS

An IA to assess the primary efficacy endpoint will be conducted following the last patient Week 24 visit, once all subject VASI data have been cleaned and soft-locked. The IA for the primary efficacy assessment is planned for Week 24 in order to minimize the exposure of study subjects to placebo, and at the same time assess for efficacy at the earliest time point a

clinical response to treatment could be expected. Analysis outputs will be generated when the last subject has completed 24 weeks of study participation, and may include results for all planned endpoints up to Week 24. At the time of interim analysis at Week 24, the randomization will be unblinded to the sponsor and its designee. The final study database will be locked following last patient last visit at Week 64, once all subject data have been cleaned, and all coding of terms (AE, Concomitant Medications, Medical History) has been finalized.

Investigational sites, subjects, and study team members directly involved in study activities will remain blinded to study treatment assignments until the last subject completes their double-blind follow-up period (Week 64). A designated list of blinded and unblinded study personnel shall be maintained. Sharing of subject-level unblinded information for the IA will be confined to a designated unblinded study team. For the 24-week primary end-point, patient level data will not be provided to the site staff and the blinded study team. The Final CSR will be provided to the PI at the end of the study.

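### A baseline-to-Week 24 correlation above 0.5 does not make an SD of change of 6.4 conservative: 6.4 needs about 0.74, so the stated 85% power lacks its stated support

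*Protocol*

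**What the plan says.** Protocol 9.2 assumes a baseline VASI SD of 8.9, a treatment difference of 3.94, a two-sided alpha of 0.05 and 52 evaluable subjects per arm. It states: "The study is powered at 85%, and assumes a two-sample Z-test with equal variances". The variability input rests on the correlation between baseline and Week 24 scores, which is "expected to be >0.5, the standard deviation of the difference is conservatively estimated at 70% of the Baseline SD, or 6.4". SAP 3.2 repeats the reasoning: "the standard deviation of the difference is conservatively estimated at 70% of the Baseline SD, or 6.4". Neither document gives a Week 24 SD, a planning value for the correlation, or a separate source for 6.4.

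The planned analysis is not the test used for sizing. Protocol 9.8 (Efficacy Analysis) says: "The primary endpoint method of analysis will use an Analysis of Covariance (ANCOVA) model to compare change from baseline in VASI score results". SAP 6.9.1.2 lists its terms as treatment, disease stability "and baseline VASI score as a covariate".

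The documents also differ on the design that the 85% describes. SAP 3.2 says: "The sample size takes into account an interim assessment of futility and efficacy", at 75% completion of the Week 24 VASI assessment. Protocol 9.8 (Interim Analysis) says: "No formal Interim Analysis will be performed for this study". SAP 7 says: "An IA to assess the primary efficacy endpoint will be conducted following the last patient Week 24 visit".

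**The concern.** An input justified by a lower bound is conservative only if it still holds at that bound. With equal SDs at the two visits, a correlation of 0.5 leaves the SD of change equal to the baseline SD: 100% of it, not 70%. The 70% is close to sqrt(1 - 0.5) = 0.707, which is what results if the factor 2 in 2(1 - correlation) is left out. The documents do not say how the figure was reached, so this is only a possible explanation.

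The SD of 6.4 carries the power statement, and the power statement supports enrolling about 320 subjects. If a dose misses significance, readers will use the 85% to judge whether the trial could have detected the assumed effect. As written, they cannot tell which correlation, Week 24 SD, test or design that figure depends on.

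**Working it through.** **Inputs from Protocol 9.2 and SAP 3.2:** difference d = 3.94 (5.50 - 1.56); baseline SD 8.9; SD of change 6.4; 52 evaluable per arm; two-sided alpha 0.05; Z-test. **Assumed, because not given:** k = Week 24 SD / baseline SD, shown for 1.1, 1, 0.9 and 0.8. Write r for the correlation.

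**1. The plan's own figure.** Fixed-design power = Phi(d / (SD x sqrt(2/52)) - 1.96). With SD 6.4: 6.4 x 0.1961 = 1.255; 3.94 / 1.255 = 3.139; Phi(1.179) = 88.1%. In a fixed design 85% needs only 48 per arm.

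The 85% at 52 per arm is recovered if the interim in SAP 3.2 is included with a futility rule. I assumed one look at 75% information, O'Brien-Fleming-type alpha spending (one-sided 0.025; boundaries 2.34 and 2.01), and O'Brien-Fleming-type beta spending of 0.15 with a non-binding futility bound of about 1.42 that is followed. Power is then 85.1%, and 85% needs 51.9 per arm. A second spending convention (boundaries 2.26 and 2.04) gives 84.9%. Efficacy stopping alone gives about 87%.

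The largest SD that keeps 85% is 3.94 / ((1.960 + 1.036) x 0.1961) = 6.70 in a fixed design, and about 6.4 with efficacy plus futility.

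**2. SD of change implied by the correlation.** SD of change = 8.9 x sqrt(1 + k^2 - 2rk). At r = 0.5 and k = 1 this is 8.9. The minimum over all k is 8.9 x sqrt(1 - r^2), which at r = 0.5 is 7.71.

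**3. Correlation needed for 6.4.** r = (1 + k^2 - (6.4/8.9)^2) / (2k). This gives 0.77, 0.74, 0.72 and 0.70 for k = 1.1, 1, 0.9 and 0.8. Whatever k is, r must be at least sqrt(1 - (6.4/8.9)^2) = 0.695.

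**4. Fixed-design power, no interim, 52 per arm.** The ANCOVA uses residual SD = k x 8.9 x sqrt(1 - r^2).

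| Test | r | k = 1.1 | k = 1 | k = 0.9 | k = 0.8 |
|---|---|---|---|---|---|
| Change-score Z-test | 0.5 | 57% | 62% | 66% | 69% |
| Change-score Z-test | 0.6 | 67% | 71% | 75% | 78% |
| Change-score Z-test | 0.7 | 79% | 83% | 86% | 88% |
| ANCOVA | 0.5 | 66% | 74% | 82.5% | 90% |
| ANCOVA | 0.6 | 73% | 81% | 88% | 94% |
| ANCOVA | 0.7 | 82% | 88.5% | 94% | 98% |

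At r = 0.5 the Z-test reaches at most 74%, at the minimum SD of 7.71. With equal SDs it reaches 85% only from r = 1 - 6.70^2 / (2 x 8.9^2) = 0.72.

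**5. A scenario tied to the plan's mean changes.** Suppose the SD falls in proportion to the assumed mean improvements of 35% and 10%, so k = 0.65 on active and 0.90 on placebo (an assumption). At r = 0.5 the ANCOVA pooled SD is 6.05 and power is 91%. The change-score pooled SD is 8.16 and power is 69%.

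**6. With the assumed efficacy-plus-futility interim.** An SD of 8.9 gives about 57%, and an SD of 7.71 about 70%.

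**7. The percentage.** 0.70 x 8.9 = 6.23, while 6.4 / 8.9 = 0.72. Using 6.4 rather than 6.23 errs on the safe side (88.1% against 89.7%, fixed design).

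**The case against.** The algebra is hard to dispute. The case on the other side concerns weight, and it has five parts.

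- **0.5 is a floor, not a planning value.** A correlation of 0.74 also exceeds 0.5, so the two statements do not contradict each other. This is true, and for that reason the finding is not that the trial is underpowered. But calling 6.4 conservative on the strength of that floor claims that it holds at the floor, and it does not.
- **The planned test is ANCOVA, which usually does better.** This stands. With equal SDs it reaches 85% at a correlation of about 0.66, and at a correlation of 0.5 it reaches 85% if k is about 0.87 or less. Sizing on a simpler test is ordinary practice. The gain depends on a Week 24 SD that neither document states, and with equal SDs at 0.5 the ANCOVA residual SD is 7.71, still above 6.4.
- **The primary analysis is ITT with multiple imputation using Week 12 VASI, so 52 understates the information.** Some information will be recovered. Even full recovery to 64 per arm gives only 71% (Z-test) and 82% (ANCOVA) at a correlation of 0.5 with equal SDs, and 52 is the documents' own sizing number.
- **SAP 3.2 names its design, and 85% follows from 6.4 under it.** This also stands, given an assumed futility rule. But the Protocol excludes a formal interim, and SAP 7 places its analysis after all Week 24 data are in, so the two documents together do not settle which design the 85% belongs to.
- **Nothing in conduct or inference changes.** Correct, and this limits the consequence to the stated rationale.

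**Conclusion.** The concern holds. The step from a correlation above 0.5 to a conservative SD of 6.4 is false as written in both documents. At 0.5 the SD of change is 8.9 with equal SDs and never below 7.71; 6.4 needs about 0.74 with equal SDs and at least 0.695 in any case. These results follow from the variance identity and the stated baseline SD alone.

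The size of the power gap is less certain. For the stated Z-test at 0.5 there is a shortfall at every SD ratio. For the planned ANCOVA it depends on the ratio, and the range of 1.1 to 0.8 is my assumption. Figures with an interim also rest on assumed spending and futility rules. What fails is the justification of the 85%, not the estimate, the test or the decision rule.

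**What to change.** Make the same changes in Protocol 9.2 and SAP 3.2:

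1. Delete the word claiming conservatism and the argument from a correlation above 0.5.
2. Give the source of 6.4 and say what it implies. Suggested text: *The SD of change in VASI at Week 24 is assumed to be 6.4 (source to be given). If the Week 24 SD equals 8.9, this implies a correlation with baseline of about 0.74; at a correlation of 0.5 the SD of change would be 8.9.* The 0.74 is a consequence of 6.4, not evidence for that correlation.
3. Restate power as a range over the correlation and the SD ratio, including ratios above 1, with each figure labelled as change-score Z-test or ANCOVA and as fixed design without interim. The table above can serve.
4. Before quoting a single power figure, reconcile the interim in SAP 3.2 with the Protocol's statement that there is none and with SAP 7. An SD of 6.4 gives 88.1% in a fixed design and about 85% only with an efficacy-plus-futility look.
5. Minor: change 70% to 72%.

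The cost is wording in two sections and one short table. Enrolment, analysis, alpha and endpoint stay as they are.
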